Appendix E. Two-parameter BLRM Design

A two-parameter Bayesian logistic regression model (BLRM, [Neuenschwander et al, 2008](#)) is used to guide dose escalation. The maximum tolerated dose (MTD) target Toxicity Probability Interval (TPI) for dose limiting toxicity (DLT) is (0.20, 0.33) and a TPI of (0.33, 1.00) is defined as excessive. The design seeks to identify a dose most likely to have a DLT rate in the target TPI, but with overdose control that limits the possibility the dose has an excessive DLT rate ([Babb et al, 1998](#)). The probability of a DLT at dose level d_i is assumed to follow a Bernoulli distribution with probability p_i where the logit of p_i increases linearly with the log of the standardized dose in the following 2-parameter logistic model:

$$\log [p_i / (1-p_i)] = \text{logit}(p_i) = \log[a] + \exp(\log[b]) \log (d_i / d_{\text{ref}})$$

where a and b are random variables and d_{ref} is one of the planned dose selected as the reference dose.

A bi-variate normal prior distribution ([Neuenschwander et al, 2008](#)) was selected for $\theta = (\log a, \log b)$ where the probability that the true DLT rate is ≤ 0.40 at 180 milligrams (mg) is 0.90 and the probability the true DLT rate is ≤ 0.05 at the reference dose (720 mg) is 0.05. Additionally, the prior is such that p_i is approximately 0.05 for the 180 mg dose and 0.25 for the reference dose.

The operating characteristics of the two-parameter BLRM design were evaluated via simulation. The cohort size was fixed to 2 or 4 subjects. The initial dose level is 180 mg and subsequent doses were selected based on the following rules:

- After each cohort, the next dose is the one with the highest probability of the target TPI, but with a less than 0.25 probability of an excessive TPI.
- Escalation to a dose level that is greater than 2x the current dose level is not allowed.

Dose escalation was stopped given 1 or more of the following conditions:

- There have been at least 6 subjects treated at the dose recommended by the model.
- A maximum number of 30 subjects are evaluated. Operating characteristics are described below.

Operating characteristics

A total of 4 planned dose levels (unit: mg) were considered: 180, 360, 720 and 960.

Two intermediate dose levels were also considered: 270 and 540 mg. The design was evaluated for 4 possible dose-response scenarios: Low MTD, Mid MTD, High MTD and

a scenario where none of the planned dose levels are tolerable. [Table 16](#) shows the dose level and true probability of DLT for each scenario used in the simulated studies estimating the MTD. [Table 17](#) reports the operating characteristics from 1000 simulated studies estimating the MTD when the target TPI is (0.20, 0.33). The rate of MTD selected and the number of subjects assigned to each dose level are presented in [Table 18](#).

Table 16. True Probability of DLT by Scenario for Simulated Studies Estimating MTD

Dose Level	180	270	360	540	720	960
MTD Scenario						
High	0.01	0.01	0.05	0.15	0.25	0.33
Mid	0.05	0.15	0.25	0.33	0.43	0.53
Low	0.15	0.25	0.33	0.43	0.53	0.63
No tolerable dose levels	0.35	0.43	0.50	0.58	0.65	0.73

DLT = dose-limiting toxicity; MTD = maximum tolerated dose

Approved

Table 17. Operating Characteristics by Scenario for Simulated Studies Estimating the MTD When the Target TPI is (0.20, 0.33)

MTD Scenario	High		Mid		Low		No tolerable dose levels	
	4	2	4	2	4	2	4	2
Subjects per cohort	4	2	4	2	4	2	4	2
Number of Subjects	20 (16 to 24)	12 (12 to 14)	20 (16 to 24)	12 (10 to 14)	16 (12 to 20)	10 (2 to 14)	8 (4 to 12)	2 (2 to 8)
Median (IQR)								
Number of DLTs	2 (2 to 4)	2 (1 to 2)	4 (3 to 5)	3 (2 to 3)	4 (3 to 6)	2 (1 to 4)	3 (2 to 4)	2 (1 to 3)
Median (IQR)								
Proportion of DLT (%)	12.5 (10 to 17)	14.3 (8 to 19)	25.0 (19 to 25)	25.0 (19 to 35)	26.7 (25 to 37)	37.5 (25 to 50)	50.0 (37 to 50)	50.0 (43 to 50)
Median (IQR)								
Percentage of studies recommending dose with DLT probability of:								
≤ 10%	4.6	9.2	11.2	25.9	29.7*	53.6*	82.3*	89.3*
> 10% and ≤ 20%	47.2	55.6	4.6	2.0	10.3	0.9	NA	NA
> 20% and ≤ 33%	48.2	35.2	78.2	64.3	47.5	30.3	NA	NA
> 33%	NA	NA	6.0	7.8	12.5	15.2	17.7	10.7
Probability of identifying MTD to have 15% to 33% DLT probability	95.4	90.8	82.8	66.3	57.8	31.2	NA	NA

DLT = dose-limiting toxicity; IQR = interquartile range; MTD = maximum tolerated dose; TPI = toxicity probability interval; NA=not applicable

* In the low MTD scenario and the scenario where all planned dose levels are intolerable, this represents the percent of studies declaring all planned dose levels as not tolerable.

Approved

Table 18. Rate of MTD Selected and Number of Subjects Assigned at Each Dose Level by Scenario

MTD Scenario	High		Mid		Low		No tolerable dose levels	
	4	2	4	2	4	2	4	2
Rate of MTD selected at each dose level (%):								
Below lowest dose	0.2	2.6	8.1	25.0	29.7	53.6	82.3	89.3
180 mg	0.1	0.0	3.1	0.9	10.3	0.9	9.2	0.9
270 mg	0.0	0.0	4.6	2.0	9.0	2.2	3.2	1.0
360 mg	4.3	6.6	43.8	31.3	38.5	28.1	4.7	7.4
540 mg	47.2	55.6	34.4	33.0	10.8	14.3	0.5	1.4
720 mg	44.3	33.2	5.2	7.8	1.6	0.9	0.1	0.0
960 mg	3.9	2.0	0.8	0.0	0.1	0.0	0.0	0.0
Average number of subjects at each dose level								
180 mg	4.1	2.0	4.7	2.3	5.3	2.4	5.1	2.4
270 mg	0.2	0.2	1.6	0.8	2.1	0.9	1.4	0.5
360 mg	4.3	2.5	6.0	3.5	5.1	3.1	1.6	1.7
540 mg	5.3	4.3	4.7	3.2	2.6	1.9	0.3	0.6
720 mg	5.6	3.3	1.8	1.4	0.7	0.5	0.1	0.1
960 mg	0.5	0.2	0.2	0.0	0.1	0.0	0.0	0.0

MTD = maximum tolerated dose.

Approved

Operating Characteristics for Standard 3+3 Design

As a comparison, the operating characteristics from 1000 simulated studies estimating the MTD when using a standard 3+3 design are reported in [Table 19](#).

Table 19. Operating Characteristics by Scenario for Simulated Studies Estimating the MTD Using a 3+3 Design

MTD Scenario	High	Mid	Low	No tolerable dose levels
Number of Subjects	15	12	12	6
Median (IQR)	(12 to 18)	(12 to 15)	(9 to 13)	(3 to 12)
Number of DLTs	2	3	3	3
Median (IQR)	(2 to 3)	(2 to 4)	(2 to 4)	(2 to 3)
Proportion of DLT (%)	16.7	23.8	26.7	33.3
Median (IQR)	(11 to 20)	(20 to 27)	(22 to 33)	(33 to 67)
Percentage of studies recommending dose with DLT probability of:				
≤ 10%	44.7	43.5	19.4*	65.9*
> 10% and ≤ 20%	0.0	0.0	47.4	NA
> 20% and ≤ 33%	55.3	43.3	29.5	NA
> 33%	NA	13.2	3.7	34.1
Probability of identifying MTD to have 15% to 33% DLT probability	55.3	43.3	76.9	NA

DLT = dose-limiting toxicity; IQR = interquartile range; MTD = maximum tolerated dose; NA=not applicable
 * In the low MTD scenario and the scenario where all planned dose levels are intolerable, this represents the percent of studies declaring all planned dose levels as not tolerable.

Approved

Appendix F. Hepatotoxicity Stopping Rules: Suggested Actions and Follow-up Assessments and Study Treatment Rechallenge Guidelines

Subjects with abnormal hepatic laboratory values (ie, alkaline phosphatase [ALP], aspartate aminotransferase [AST], alanine aminotransferase [ALT], total bilirubin [TBL]) and/or international normalized ratio (INR) and/or signs/symptoms of hepatitis (as described below) may meet the criteria for withholding or permanent discontinuation of Amgen investigational product or other protocol-required therapies, as specified in the *Guidance for Industry Drug-Induced Liver Injury: Premarketing Clinical Evaluation, July 2009*.

Criteria for Withholding and/or Permanent Discontinuation of Amgen Investigational Product and Other Protocol-required Therapies Due to Potential Hepatotoxicity

The following stopping and/or withholding rules apply to subjects for whom another cause of their changes in liver biomarkers (TBL, INR and transaminases) has not been identified.

Important alternative causes for elevated AST/ALT and/or TBL values include, but are not limited to:

- Hepatobiliary tract disease
- Viral hepatitis (eg, hepatitis A/B/C/D/E, Epstein-Barr Virus, cytomegalovirus, herpes simplex virus, varicella, toxoplasmosis, and parvovirus)
- Right sided heart failure, hypotension or any cause of hypoxia to the liver causing ischemia
- Exposure to hepatotoxic agents/drugs or hepatotoxins, including herbal and dietary supplements, plants and mushrooms
- Heritable disorders causing impaired glucuronidation (eg, Gilbert's syndrome, Crigler-Najjar syndrome) and drugs that inhibit bilirubin glucuronidation (eg, indinavir, atazanavir)
- Alpha-one antitrypsin deficiency
- Alcoholic hepatitis
- Autoimmune hepatitis
- Wilson's disease and hemochromatosis
- Nonalcoholic fatty liver disease including steatohepatitis
- Non-hepatic causes (eg, rhabdomyolysis, hemolysis)

If investigational product(s) is/are withheld, the subject is to be followed for possible drug induced liver injury (DILI) according to recommendations in the last section of this appendix.

Rechallenge may be considered if an alternative cause for impaired liver tests (ALT, AST, ALP) and/or elevated TBL, is discovered and the laboratory abnormalities resolve to normal or baseline (see next section in this appendix).

Table 20. Conditions for Withholding and/or Permanent Discontinuation of Amgen Investigational Product and Other Protocol-required Therapies Due to Potential Hepatotoxicity

Analyte	Temporary Withholding	Permanent Discontinuation
TBL	> 3x ULN at any time	> 2x ULN
INR	--	> 1.5x (for subjects not on anticoagulation therapy)
AST/ALT	> 8x ULN at any time > 5x ULN but < 8x ULN for ≥ 2 weeks > 5x ULN but < 8x ULN and unable to adhere to enhanced monitoring schedule > 3x ULN with clinical signs or symptoms that are consistent with hepatitis (such as right upper quadrant pain/tenderness, fever, nausea, vomiting, and jaundice)	In the presence of no important alternative causes for elevated AST/ALT and/or TBL values > 3x ULN (when baseline was < ULN)
ALP	> 8x ULN at any time	--

ALP = alkaline phosphatase; ALT = alanine aminotransferase; AST = aspartate aminotransferase; INR = international normalized ratio; TBL = total bilirubin; ULN = upper limit of normal

Criteria for Rechallenge of Amgen Investigational Product and Other Protocol-required Therapies After Potential Hepatotoxicity

The decision to rechallenge the subject is to be discussed and agreed upon unanimously by the subject, investigator, and Amgen.

If signs or symptoms recur with rechallenge, then [Amgen investigational product and other protocol-required therapies, as appropriate] is to be permanently discontinued. Subjects who clearly meet the criteria for permanent discontinuation (as described in [Table 20](#)) are never to be rechallenged.

Approved

Drug-induced Liver Injury Reporting and Additional Assessments

Reporting

To facilitate appropriate monitoring for signals of DILI, cases of concurrent AST or ALT and TBL and/or INR elevation, according to the criteria specified in the above, require the following:

- The event is to be reported to Amgen as a serious adverse event within 24 hours of discovery or notification of the event (ie, before additional etiologic investigations have been concluded)
- The appropriate Case Report Form (CRF) (eg, Event CRF) that captures information necessary to facilitate the evaluation of treatment-emergent liver abnormalities is to be completed and sent to Amgen

Other events of hepatotoxicity and potential DILI are to be reported as serious adverse events if they meet the criteria for a serious adverse event defined in [Section 9.1.2](#).

Additional Clinical Assessments and Observation

All subjects in whom investigational product(s) or protocol-required therapies is/are withheld (either permanently or conditionally) due to potential DILI as specified in [Table 20](#) or who experience AST or ALT elevations > 3 x upper limit of normal (ULN) or 2-fold increases above baseline values for subjects with elevated values before drug are to undergo a period of “close observation” until abnormalities return to normal or to the subject’s baseline levels.

Assessments that are to be performed during this period include:

- Repeat AST, ALT, ALP, bilirubin (BIL) (total and direct), and INR within 24 hours
- In cases of TBL > 2x ULN or INR > 1.5, retesting of liver tests, BIL (total and direct), and INR is to be performed every 24 hours until laboratory abnormalities improve

Testing frequency of the above laboratory tests may decrease if the abnormalities stabilize or the investigational product(s) or protocol-required therapies has/have been discontinued AND the subject is asymptomatic.

Initiate investigation of alternative causes for elevated AST or ALT and/or elevated TBL.

The following are to be considered depending on the clinical situation:

- Complete blood count with differential to assess for eosinophilia
- Serum total immunoglobulin (Ig)G, anti-nuclear antibody anti-smooth muscle antibody, and liver kidney microsomal antibody-1 to assess for autoimmune hepatitis

- Serum acetaminophen (paracetamol) levels
- A more detailed history of:
 - Prior and/or concurrent diseases or illness
 - Exposure to environmental and/or industrial chemical agents
 - Symptoms (if applicable) including right upper quadrant pain, hypersensitivity-type reactions, fatigue, nausea, vomiting and fever
 - Prior and/or concurrent use of alcohol, recreational drugs and special diets
 - Concomitant use of medications (including non-prescription medicines and herbal and dietary supplements), plants, and mushrooms
- Viral serologies
- Creatine phosphokinase, haptoglobin, lactate dehydrogenase and peripheral blood smear
- Appropriate liver imaging if clinically indicated
- Appropriate blood sampling for pharmacokinetic analysis if this has not already been collected
- Hepatology consult (liver biopsy may be considered in consultation with a hepatologist)

Follow the subject and the laboratory tests (ALT, AST, TBL, INR) until all laboratory abnormalities return to baseline or normal or considered stable by the investigator. The “close observation period” is to continue for a minimum of 4 weeks after discontinuation of all investigational product(s) and protocol-required therapies.

The potential DILI event and additional information such as medical history, concomitant medications and laboratory results must be captured in the corresponding CRFs.

Approved

Summary of Changes Protocol Amendment 1 to Amendment 3

Protocol Title: A Phase 1/2, Open-label Study Evaluating the Safety, Tolerability, Pharmacokinetics, Pharmacodynamics, and Efficacy of AMG 510 Monotherapy in Subjects With Advanced Solid Tumors With *KRAS p.G12C* Mutation and AMG 510 Combination Therapy in Subjects With Advanced NSCLC With *KRAS p.G12C* Mutation

Amgen Protocol Number (AMG 510) 20170543

EudraCT Number 2018-001400-11

NCT Number NCT03600883

Amendment Dates: 28 March 2019 and 22 May 2019

Rationale for Protocol Amendment 1 to Superseding Protocol Amendment 2:

The main change for Protocol Amendment 2 is the addition of the phase 2 portion of the study. The ongoing phase 1 portion was also amended as described below.

The protocol is being amended to incorporate changes in the study design as follows:

Overall, the addition of the phase 2 and the updates to the ongoing phase 1 portion of the study required updates across multiple sections of protocol including but not limited to the following: Protocol Synopsis, Study Schemas, Objectives and Endpoints ([Section 1.0](#)), Hypothesis ([Section 2.7](#)), Experimental Plan ([Section 3.0](#)), Subject Eligibility ([Section 4.0](#)), Treatment Procedures ([Section 7.0](#)), Schedule of Assessments ([Section 7.1](#)), Study Procedures ([Section 7.2](#)) and Statistical Considerations ([Section 10](#)). The first in human (FIH) portion of the study will continue as planned and in the protocol is noted as the Phase 1 portion.

Phase 2:

- Phase 2 is a multicenter, non-randomized, open-label study to evaluate efficacy and safety/tolerability of AMG 510 as monotherapy in subjects with *KRAS p.G12C* mutant advanced solid tumors (NSCLC, CRC, and other tumors)

Updates to Phase 1:

- A phase 1, BID cohort was added to evaluate initial safety, PK and pharmacodynamics of AMG 510

- [REDACTED]
- [REDACTED]
- [REDACTED]
- Modify the phase 1 dose expansion cohort (part 2a) to allow enrollment of subjects with any tumor type into 1 cohort of up to 60 subjects
- Clarify that the backfill enrollment in phase 1 part 1a will be expanded up to 40 subjects
- Add details on the subjects being enrolled in the phase 1 part 1a portion of the study at sites in Japan

Additional changes to the protocol include:

- Update the number sites that will be included in the study
- Update RECIST text to align with the RECIST templated language.
- Removal of self-evident corrections language
- Administration, typographical, and formatting changes were made throughout the protocol

Rationale for Superseding Protocol Amendment 2 to Protocol Amendment 3:

The protocol is being amended to incorporate following key changes in the study design based on the feedback received from the regulatory agency on protocol amendment 2:

Updates to Phase 1:

- Sample size justification is provided for enrollment up to 60 subjects in phase 1 expansion portion.
- Futility/efficacy thresholds are added to monitor antitumor activities in phase 1 expansion to provide guidance to DLRM for determining RP2D and continuing to phase 2.
- Revision to use standard RECIST 1.1 for analysis of tumor response.

Updates to Phase 2:

- Revised patient population for NSCLC and CRC as defined by the eligibility criteria in terms of the extent of prior therapies.
- Clarified that twice-daily dosing cohort (phase 1 part 1b) will only be initiated after completion of preliminary food effect evaluation.
- Sample sizes for NSCLC, CRC are adjusted based on new benchmark rates
 - For NSCLC, revised the benchmark rate to 23% to exclude from the lower limit of the 95% confidence interval for observed ORR.
 - For CRC, revised the benchmark rate to 10% to exclude from the lower limit of the 95% confidence interval for observed ORR.

- Clarified that efficacy analysis will be performed using only “Phase 2” portion. Language pertaining to pooling subjects at RP2D from phase 1 and phase 2 for efficacy analysis is removed.
- Removed interim analysis for efficacy.
- Futility interim analysis in phase 2 portion is updated to allow continuous monitoring using Bayesian predictive probability method.
- Revision to use standard RECIST 1.1 for analysis of tumor response.
- Additional changes were made to the protocol with the following rationales.
- Time to response was added as an secondary endpoint in all phases to describe timing aspect of AMG 510 response profile.
- Removed the inclusion criteria requirement for alkaline phosphatase . Alkaline phosphatase (ALP) is often elevated in advance solid tumor with bone or liver metastasis and may not reflect liver function required to participate in the clinical trial when other liver function parameter criteria (AST, ALT, INR, Bilirubin) are met.
- Clarification of the inclusion criteria 215 pertaining birth control methods in accordance to Clinical Trial Facilitation and Coordination Gropu (CTFG) guidance.
- [REDACTED]
- [REDACTED]
- [REDACTED]
- [REDACTED]
- [REDACTED]
- [REDACTED]
- [REDACTED]
- [REDACTED]
- Additional patient-reported outcomes (NSCLC SAQ and GP5 FACT-G) were added to fully understand the impact of treatment on patients from their perspective.
- Addition of urine pregnancy test on day 1 of every cycle in female subjects with child bearing potential to meet CTFG guidance related to pregnancy testing in clinical trials.

Statistical Analysis Plan

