Phase 2 is a multicenter, non-randomized, open-label, phase 2 study to evaluate efficacy and safety/tolerability of AMG 510 as monotherapy in subjects with *KRAS p.G12C* mutant advanced solid tumors (NSCLC, CRC, and other tumors).

Administration of AMG 510 may continue **until subject has confirmed disease progression, or discontinues from the treatment for reasons listed in Section 8.3.1.**

Phase 1:

Dose Exploration – Part 1

Part 1a Monotherapy Cohorts (Once Daily Dosing – QD):

Dose exploration monotherapy cohorts will estimate the MTD, and evaluate the safety, tolerability, PK, and pharmacodynamics of different doses of AMG 510 administered orally once daily in subjects with *KRAS p.G12C* mutant advanced solid tumors. Enrollment into the dose exploration cohorts may be from any eligible solid tumor type. Dose escalation will begin with 2-4 subjects treated at the lowest planned dose level of 180 mg. Dose escalation will follow the planned schedule with 2-4 subjects treated in each cohort. If no DLT is observed, dose escalation will continue to the next planned dose cohort as per [Table 1](#). **In addition to the dose levels outlined in Table 1, intermediate doses of 270 mg and 540 mg may be explored.** Upon escalation to the next planned dose cohort, sentinel dosing will apply. There will be a 2-day window between the first subject dosed and subsequent subjects. Once a subject experiences a DLT, dosing for subsequent cohorts will be recommended using the dose level recommendation from the BLRM. The decision to advance to the next dose level will be recommended by the Dose Level Review Team (DLRT) using the dose level recommendation from BLRM, as appropriate, and by evaluating available safety data, laboratory, and PK information.

Approved

Intra-subject dose escalations are allowed on this study. Subjects who complete the DLT period may proceed to a higher dose level for the following treatment cycle if the next dose cohort is deemed safe at that time by the DLRT and after consultation with the sponsor if:

- no DLT has been reported for this subject during or after completion of the DLT period
- the subject has not experienced any \geq grade 2 adverse events (deemed treatment related by the investigator) during treatment

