3.1.1.1.1 Part 1a Monotherapy Cohorts (Once Daily Dosing – QD)

Dose exploration monotherapy cohorts will estimate the MTD or R2PD and evaluate the safety, tolerability, PK, and pharmacodynamics of different doses of AMG 510 administered orally QD in subjects with *KRAS p.G12C* mutant advanced solid tumors. Enrollment into the dose exploration cohorts may be from any eligible *KRAS p.G12C* mutant solid tumor type. Dose escalation will begin with 2-4 subjects treated at the lowest planned dose level of 180 mg. Dose escalation will follow the planned schedule with 2-4 subjects treated in each cohort. If no DLT is observed, dose escalation will

Approved

continue to the next planned dose cohort as per [Table 1](#). **In addition to the dose levels outlined in [Table 1](#), intermediate doses of 270 mg and 540 mg may be explored.**

Upon escalation to the next planned dose cohort, sentinel dosing will apply. There will be a 2 day window between the first subject dosed and subsequent subjects. Once a subject experiences a DLT, dosing for subsequent cohorts will be recommended using the dose level recommendation from the BLRM. After each cohort, the model's recommended MTD dose level for evaluation is the dose level with the highest probability of the target toxicity probability interval (TPI), but with a less than 0.25 probability of an excessive TPI. The target TPI is (0.20, 0.33], and a TPI of (0.33, 1.00] is defined as excessive. The decision to advance to the next dose level will be recommended by the DLRT using the dose level recommendation from BLRM, as appropriate, and by evaluating available safety data, laboratory, and PK information.

Intra-subject dose escalations are allowed in this study. Subjects who complete the DLT period may proceed to a higher dose level for the following treatment cycle if the next dose cohort is deemed safe at that time by the DLRT and after consultation with the sponsor if:

- no DLT has been reported for this subject during or after completion of the DLT period
- the subject has not experienced any \geq grade 2 adverse events (deemed treatment related by the investigator) during treatment

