Subjects who proceed to a higher dose level will be required to have back to back clinic visits on day 1 and day 2 at the beginning of the cycle with the higher dose. The safety assessments of chemistry and urinalysis will be performed on day 1 and day 2. A repeat of PK sample collection will be performed as on cycle 1 day 1 and cycle 1 day 2, regardless of actual study cycle.

Subjects who do not proceed to a higher dose may continue to receive additional cycles at the original dose.

Dose exploration will continue until any of the following events.

- The highest planned dose level is determined to be safe and tolerable (minimum of 6 DLT-evaluable subjects).
- The MTD is identified, BLRM recommends a dose level which already has 6 DLT-evaluable subjects.

Japanese subjects will be enrolled in the dose exploration portion of the study and treated at the MTD or RP2D.

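### Tables 17 and 18 simulate a model-chosen dose after every cohort, whereas Part 1a as written steps to the next planned dose until a first DLT, so the printed 960 mg exposure is not that of the written rule

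*Supplement*

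**What the plan says.** **The simulated design (protocol Amendment 3, Appendix E).** "After each cohort, the next dose is the one with the highest probability of the target TPI", subject to a probability below 0.25 that the DLT rate is excessive. Six doses are available to the model: 180, 270, 360, 540, 720 and 960 mg. "The cohort size was fixed to 2 or 4 subjects". "Escalation to a dose level that is greater than 2x the current dose level is not allowed". Simulated escalation stops when "There have been at least 6 subjects treated at the dose recommended by the model", or when 30 subjects have been evaluated.

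**The written escalation rule (synopsis Part 1a; protocol 3.1.1.1.1; repeated in SAP Amendment 1, 3.1).** "If no DLT is observed, dose escalation will continue to the next planned dose cohort as per" Table 1, which lists 180, 360, 720 and 960 mg. The 270 and 540 mg doses are optional. The model enters as follows: "Once a subject experiences a DLT, dosing for subsequent cohorts will be recommended using the dose level recommendation from the BLRM". One of the two events that end dose exploration is: "The highest planned dose level is determined to be safe and tolerable (minimum of 6 DLT-evaluable subjects"). Appendix E does not list that rule.

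**Text that points the other way.** Directly after the first-DLT sentence, 3.1.1.1.1 describes the model's recommended dose after each cohort, with the same 0.25 limit. The synopsis (Statistical Considerations), protocol 10.4.1.1 and SAP 7.1.1 have the BLRM inform dosing decisions without a first-DLT condition. Protocol 6.1.1.2 lets the dose level review team recommend an intermediate dose, repeat a cohort or delay.

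**The concern.** Appendix E presents its tables as the operating characteristics of an escalation with overdose control. Under the written lead-in, that control is not stated to govern dosing until a DLT has occurred. The two rules part company on the path with no DLTs. Protocol 2.6.2.1 reports that path: no DLT in 6, 12 and 4 subjects at 180, 360 and 720 mg, after which the review team allowed 4 subjects at 960 mg.

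If the simulated rule and the written rule lead to different doses, the printed MTD selection rates, sample sizes and numbers of subjects per dose belong to a design other than the one in 3.1.1.1.1. The top dose is where this shows most.

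**Working it through.** **1. What the printed figures are.** Table 17 is built from the same simulation as Table 18. Its bands are sums of Table 18's selection rates:
- High, cohorts of 4, DLT rate >20% to 33%: 44.3 (720 mg) + 3.9 (960 mg) = 48.2, as printed.
- High, cohorts of 2, same band: 33.2 + 2.0 = 35.2, as printed.
- Mid, cohorts of 4, >33%: 5.2 + 0.8 = 6.0, as printed.

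Table 17 gives no number of subjects at 960 mg. Only Table 18 does, under "Average number of subjects at each dose level".

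**2. Can Table 18 be recovered from Appendix E's rule?** Only approximately, because the standard deviation of log b and the correlation are not printed. Simulating the Appendix E rule under four priors that meet the stated constraints gave 960 mg averages of 0.37 to 0.50 (High, cohorts of 4; printed 0.5) and 0.05 to 0.31 (High, cohorts of 2; printed 0.2). A prior with SD 0.87 and correlation -0.8 gave 1.76 and 1.10, but it did not match the printed selection rates in High with cohorts of 4 (15% and 69% at 540 and 720 mg, against 47% and 44%). The table is compatible with the Appendix E rule, but the match depends on the prior. Nothing below uses a prior.

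**3. The written no-DLT step, using Table 16 alone.** With cohort size c, the 960 mg cohort opens without any DLT when all c subjects at 180, 360 and 720 mg are free of DLTs:

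P = [(1 - p180)(1 - p360)(1 - p720)]^c

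Mean number of subjects in that first 960 mg cohort = c x P.

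Bracketed products from Table 16:
- High: 0.99 x 0.95 x 0.75 = 0.7054
- Mid: 0.95 x 0.75 x 0.57 = 0.4061
- Low: 0.85 x 0.67 x 0.47 = 0.2677

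| Scenario | c | P | c x P | Table 18 |
|---|---|---|---|---|
| High | 2 | 0.498 | 1.00 | 0.2 |
| High | 4 | 0.248 | 0.99 | 0.5 |
| Mid | 2 | 0.165 | 0.33 | 0.0 |
| Mid | 4 | 0.027 | 0.11 | 0.2 |
| Low | 2 | 0.072 | 0.14 | 0.0 |
| Low | 4 | 0.005 | 0.02 | 0.1 |

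The High ratio with cohorts of 2 is 0.995/0.2 = 5.0. Since 0.2 may stand for 0.15 to 0.25, the range is 4.0 to 6.6. With cohorts of 4 the ratio is 0.99/0.5 = 2.0.

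**4. Is this simulation noise?** No. Over 1000 trials, the standard error of the High value with cohorts of 2 is 2 x sqrt(0.498 x 0.502 / 1000) = 0.03.

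**5. Does the two-fold escalation cap explain it?** No. The Table 1 steps are 2.0, 2.0 and 1.33 times the previous dose, so the cap never blocks them.

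**6. What the bound leaves out.** It counts one cohort only. Further 960 mg subjects, whether to reach 6 DLT-evaluable or because the BLRM returns there after a DLT, would add to it.

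**The case against.** **The BLRM may already apply from the first cohort.** The passages without a first-DLT condition, and the after-each-cohort sentence inside 3.1.1.1.1, support this. A reader might infer from the first-DLT sentence that escalation runs with no model input; the documents do not support that. The objection moves the fault without removing it. If the BLRM governs throughout, the no-DLT step in the synopsis and 3.1.1.1.1 is misstated. If it does not, the tables describe another design.

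**The step is not automatic.** The review team votes and may choose an intermediate dose. That is correct, so the figures above bound a literal reading and do not predict conduct. But the team's discretion was not simulated either, so it does not validate the tables.

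**The largest ratio is not overdosing.** This stands. In High, 960 mg has a true rate of 0.33, within the target interval (0.20, 0.33]. Among the three gaps in the brief, only Mid with cohorts of 2 involves an excessive rate (0.53), and it amounts to 0.33 subjects.

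**The gap is uneven.** This also stands. With cohorts of 4 the bound lies below the printed value in Mid and Low. The reported 720 mg group had 4 subjects, for which the High ratio is two-fold, not five-fold.

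**Little escalation remains.** 960 mg is the highest planned once-daily dose and was opened before Amendment 3. The value of a correction now lies mostly in the final MTD estimate and in an accurate record of the design.

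**Conclusion.** The concern holds in a limited form. The rule simulated in Appendix E and the no-DLT step written in the synopsis, 3.1.1.1.1 and SAP 3.1 are different rules, and other sections leave open which applies. At face value, the written step puts at least 1.00, 0.99 and 0.33 subjects on average at 960 mg, where Table 18 prints 0.2, 0.5 and 0.0 (High with cohorts of 2, High with cohorts of 4, Mid with cohorts of 2). This assumes independent subjects, fixed cohorts of 2 or 4, the Table 16 rates and no intervention by the review team.

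Two stronger readings go too far. Table 17 cannot be said to understate 960 mg exposure, since it does not report it; it only rests on the same simulation. Nor do the documents show that opening 960 mg breached the 0.25 limit. The prior is not fully printed, and the account of the January 2019 review does not say what the model gave.

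**What to change.** Make 3.1.1.1.1 (with the synopsis and SAP 3.1), 10.4.1.1 and Appendix E agree on whether the BLRM and its 0.25 limit apply before a first DLT. Which rule is right is for the sponsor and investigators to settle; this point takes no position.

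Then do one of two things:
- Re-run Tables 17 and 18 under the reconciled rule, with the role of 270 and 540 mg and both stopping rules stated, and replace the figures. Printing the prior's standard deviations and correlation would let others reproduce them.
- Keep the tables and label them as describing a rule that differs from the one in 3.1.1.1.1.

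The cost is a text reconciliation plus either a re-run of an existing simulation and two replacement tables, or a label. No subject numbers or data collection need change for this.
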